4.8 Prior and Concomitant Procedures

Prior and concomitant non-drug therapies will be summarized by System Organ Class and Preferred Term using the Medical Dictionary for Regulatory Activities (MedDRA) Version 24.0 or higher ATC class level II, and Preferred Term for each treatment group and listed using Safety set.

4.9 Treatment Compliance

The compliance rate will be assessed as: Compliance Rate (%) = (cumulative dose [mg] / planned dose [mg]) * 100.

Non-compliance is defined as taking less than 80% or more than 120% of study drug during any outpatient evaluation period (visit to visit).

A summary of treatment compliance, including the number and percentage of compliant, and non-compliant subjects, will be provided using Safety set. A by-subject listing of treatment compliance data will also be provided.

4.10 Efficacy Evaluation

4.10.1 Analysis and Data Conventions

Primary Null Hypothesis H0: proportion of subjects who do not experience all-cause hospitalization (defined as ≥ 24 hours), do not require supplemental oxygen for ≥ 24 h in response to $\text{SpO}_2 \leq 93\%$ and are alive by Day 28 in the GT0918 arm (p1) is equal to the proportion in the placebo arm (p2)

Primary Alternative Hypothesis Ha: the proportion of subjects who do not experience all-cause hospitalization (defined as ≥ 24 hours), do not require supplemental oxygen for ≥ 24 h in response to $\text{SpO}_2 \leq 93\%$ and are alive by Day 28 in GT0918 arm (p1) is greater than the proportion in the placebo arm 2 (p2)

Mathematically written as:

$$H_0: p_1 - p_2 = 0$$

$$H_a: p_1 - p_2 > 0$$

The primary endpoint event rate will be compared between treatment and placebo arm using Cochran–Mantel–Haenszel (CMH) Chi-square test using age and the stratification factors at time of randomization at the one-sided 0.025 level based on mITT set. P-values and 95% exact confidence intervals for the treatment difference will be presented. The actual alpha level used for the final analysis will take into account the adjustment required for the interim analysis.

4.10.1.1 Handling of Dropouts or Missing Data

4.10.1.1.1 Handling for Primary Endpoints

No dropouts will be replaced. Every effort will be made to avoid missing data. The extra effort to contact all subjects specifically those who discontinued treatment early to assess the occurrence of any component of the primary endpoint, hospitalization, need for oxygen, or death by day 28 will minimize missing data for the primary endpoint. Subjects with missing primary assessments by day 28 will be treated as meeting the primary endpoint (i.e., not experiencing hospitalization (≥ 24 hours) or using supplemental oxygen in response to $\text{SpO}_2 \leq 93\%$ (≥ 24 hours), or alive). Justification for missing primary endpoint handling is provided in Section 4.10.1.1.3.

4.10.1.1.2 Imputation of Partial Dates

Imputed dates will be used only to assign reported AEs and Medications to the different study periods: Screening Period, Treatment Period, Post-Treatment Period and Safety-Follow Up Period; for

determining the category for reported Medication as 'PRIOR ONLY', 'PRIOR and CONCOMITANT' or 'CONCOMITANT ONLY' and to determine if an AE is treatment emergent.

Both observed and imputed dates will be included into the analysis datasets. Dates will be displayed in listings with only the information available in the database.

Partial date imputation will follow ADaM conventions. The ADaM approach is to populate the numeric date variables with the imputed date and add a flag variable to the dataset that indicates the level of imputation.

The flag variable can contain the values: blank, 'D', 'M', 'Y' with

blank: indicates that no imputation was done,

D = 'Day': indicates that the day portion of the date is imputed,

M = 'Month': indicates that the month and day portions of the date are imputed,

Y = 'Year': indicates that the entire date (year, month, and day) is imputed.

Table 2 Partial Date Imputation Rules for AEs and Medications

Date	Missing Element	Rule
Start Date	day, month, and year	Set to the first dose date
	day, month only	If the year matches the first dose date, then impute to the month and day of the first dose date. Otherwise, assign January 1 st .
	day only	If the year and month match the first dose date, then impute to the day of the first dose date. Otherwise, assign the first day of the month.
End Date	day, month, and year	No imputation and assign a missing value
	day, month only	Set to December 31 st or last study visit, whichever occurs first.
	day only	Set to the last day of the month or last study visit, whichever occurs first.

Thus, AEs will be assumed to be treatment-emergent, unless there is clear evidence to suggest that the AE started prior to treatment.

4.10.1.1.3 Changes in missing data handling from the protocol

A change was made in handling of dropout and missing data as presented in the protocol amendment version 2.0 of Section 10.5.1.3: *For the primary analysis of the primary endpoint, patients with missing primary assessments will be included in the analysis and evaluated as treatment failure (i.e., hospitalization, supplemental oxygen use, or death).*

In the current SAP, handling of subjects with missing primary assessments by day 28 are updated to treat as meeting the primary endpoint (i.e., not experiencing hospitalization (≥ 24 hours) or using supplemental oxygen in response to $\text{SpO}_2 \leq 93\%$ (≥ 24 hours), or alive) for the following reasons. Firstly, in the latest version of Informed Consent Form (ICF), a clear statement was made to inform subjects that medical care related with hospitalization would be reimbursed by the sponsor to ensure all hospitalization events would be captured. Secondly, site-contacted subjects who were initially lost to follow-up as well as the majority of subjects in this study did not experience any hospitalization nor oxygen use through day 28. Additionally, known reasons for subjects who discontinued early from the study were related to reasons like "patient felt better" or "subject left out of town" rather than reasons related to worsening in the clinical status or treatment related adverse events. Moreover,

only less than two percent of hospitalization was observed in this study. Given the low hospitalization percentage, imputation of relatively high proportion of missing primary assessments as hospitalization could substantially bias or even lead to misleading conclusion of the treatment efficacy.

4.10.1.2 Multiple Comparisons/Multiplicity

One interim analysis is planned. The method of adjusting the Type I error rate used in this study is O'Brien and Fleming type alpha spending. The actual alpha spending will be calculated based on the actual information used for the interim analysis.

4.10.1.3 Examination of Subgroups

This study is not powered for subgroup analyses; therefore, all subgroup analyses will be treated as exploratory.

Summaries of the primary efficacy variable by treatment group and subgroup will be produced. No formal statistical analysis will be performed within subgroup. Forest plot will be used to evaluate the subgroup effects.

Subgroups may include:

- Sex (Male; Female)
- Geographic region (USA vs non-USA)
- Baseline severity of COVID-19 (Mild; Moderate)
- Age group (<50 years vs. \geq 50 years, <60 years vs. \geq 60 years)
- Race and ethnicity (Non-Hispanic White or others; Hispanic or Latino; Non-Hispanic Black)
- Baseline BMI (BMI category: Underweight; Normal; Overweight; Obesity)
- Days from symptom onset to study randomization (\leq 5 days; $>$ 5 days)
- Number of risk factors at time of randomization (0; 1-2; \geq 3)
- Vaccination status (Non; Partial Vaccinated; Fully Vaccinated)
- Days from the Positive SARS-CoV-2 Prior to First Dosing (\leq 3 days; $>$ 3 days)
- Biomarkers like C-reactive protein (CRP), ferritin, D-dimer at baseline (Low; Normal; High)
- Most common baseline viral variants (i.e., Gamma, Delta, Mu)

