4.10.3 Secondary Efficacy Variables

Hospitalization Percentage

Hospitalization percentage is defined as the percentage of subjects who experience any of the following events due to all causes by Day 28:

- Hospitalization for \geq 24 hours or
- Supplemental oxygen for \geq 24 hours in response to $\text{SpO}_2 \leq 93\%$ or
- Death

The same process used for the primary endpoint analysis will be used to compare the difference between treatment groups.

The following sensitivity analysis for hospitalization percentage will be performed among subset of mITT subjects:

- With dosing days > 7 days;
- With one or several major risk factors below:
 - Single risk factor: age (≥ 50 years; ≥ 60 years), major underlying medical conditions (overweight, obesity, hypertension, diabetes, smoking);
 - Combination of age factor in column 1 and other major underlying medical conditions in column 2 in the table below (e.g., age ≥ 50 years and/or obesity at randomization; age ≥ 60 years and/or obesity at randomization);

Age	Major underlying medical conditions
≥ 50 years	Overweight
≥ 60 years	Obesity Hypertension Diabetes Smoking

- With aged ≥ 50 years and days from symptom onset to study randomization ≤ 5 days and days from the positive SARS-CoV-2 Prior to first dosing ≤ 3 days;
- With aged ≥ 50 years and higher than normal biomarkers (CRP, Ferritin, D-dimer).

All sensitivity analyses will be conducted using one-sided CMH chi-square tests used for the primary endpoint analysis. Forest plots for the sensitivity analysis will be presented.

Change from Baseline to Days 3, 7, 14 and 28 in SARS CoV-2 Viral Load

Change of SARS-CoV-2 viral load from baseline, which will be evaluated in log base 10 scale, will be summarized, and plotted by treatment group and listed. Two sample t-tests will be used to compare differences in the change of SARS-CoV-2 viral load between treatment groups at Day 3, 7, 14 and 28, respectively.

Also, an analysis of covariance (ANCOVA) model will be used to compare the change from baseline in SARS-CoV-2 viral load at Day 3 with fixed effects for treatment group, age and stratification factors (sex, race and ethnicity, and number of risk factors), and baseline viral load as a covariate. If systematic pattern is identified from the residual of predicted values, a transformation of the baseline viral load will be employed to improve the performance of the model. Estimated treatment differences

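### SAP 4.10.3 plans about 21 to 31 one-sided tests in baseline-defined subsets as sensitivity analyses, against the SAP's own rule of no formal testing within subgroups

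*SAP*

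**What the plan says.** **Subgroup rule.** SAP 4.10.1.3: "This study is not powered for subgroup analyses; therefore, all subgroup analyses will be treated as exploratory", followed by "No formal statistical analysis will be performed within subgroup". Subgroup results for the primary variable are to be summarised and shown in a forest plot. Protocol 10.5.1.4 gives them the same exploratory status.

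**Subset tests.** SAP 4.10.3 introduces the list with "The following sensitivity analysis for hospitalization percentage will be performed among subset of mITT subjects". The list contains:

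- "With dosing days > 7 days"
- seven single factors: smoking, diabetes, hypertension, obesity, overweight, and two age cut-offs (50 and 60)
- "Combination of age factor in column 1 and other major underlying medical conditions in column 2 in the table below", with *and/or* used in the two worked examples
- age 50 or over together with the onset and positive-test windows
- age 50 or over together with raised CRP, ferritin or D-dimer

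The method is fixed: "All sensitivity analyses will be conducted using one-sided CMH chi-square tests used for the primary endpoint analysis". Forest plots are planned here too.

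**Endpoint tested.** "Hospitalization percentage is defined as the percentage of subjects who experience any of the following events due to all causes by Day 28". The components are those of the primary endpoint: hospitalization of at least 24 hours, supplemental oxygen of at least 24 hours for low saturation, or death.

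**Multiplicity.** SAP 4.10.1.2 covers only the interim look, through O'Brien-Fleming-type alpha spending.

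**The concern.** A sensitivity analysis asks whether the answer to one question survives other assumptions about the data. Restricting to, say, patients aged 60 or over with diabetes asks about a different population, so it is a subgroup analysis. The same patient groups are left untested in one section and tested with the primary method in another, under a label that suggests support for the primary result.

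Two things are at stake. First, the analyst cannot follow both sections. Second, a sizeable family of unadjusted one-sided tests will be produced, and a single nominally significant subset may be read as robustness of the primary finding when it reflects chance.

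**Working it through.** **1. The plan's own figures.** The SAP gives neither a count of subset tests nor an error rate for them. Its design figures (SAP 4.12: 97% v 91% event-free, one-sided 0.025, 668 subjects, about 90% power) do reproduce:

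n per arm = [1.960·√(2·0.94·0.06) + 1.282·√(0.97·0.03 + 0.91·0.09)]² / 0.06² = 328, or 656 in a fixed design.

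With one O'Brien-Fleming-type look at half the information, power at 668 is 90.3–90.8%. The design's average event frequency is (3% + 9%)/2 = 6%.

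**2. Is it the same outcome?** The hospitalization percentage equals 100% minus the primary endpoint percentage: same components, all causes, same Day 28 limit. A CMH statistic for an event is the negative of that for its absence. The tests in 4.10.3 are therefore within-subset tests of the primary outcome.

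**3. Are they the same groups?**

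| Subset variable in 4.10.3 | Listed as a subgroup in 4.10.1.3? |
|---|---|
| Age 50 and age 60 cut-offs | Yes |
| Overweight, obesity | Yes (BMI categories) |
| Symptom onset ≤ 5 days, positive test ≤ 3 days | Yes |
| CRP, ferritin, D-dimer | Yes |
| Hypertension, diabetes, smoking | No |
| Age-condition combinations | No |

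**4. Count of baseline-defined subsets.**

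- Single factors: 2 age cut-offs + 5 conditions = 7
- Age-condition pairs: 2 × 5 = 10, or 20 if *and* and *or* are both run
- Age plus timing: 1
- Age plus biomarker: 3, or 1 if the markers form one composite

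Total: 7 + 10 + 1 + 3 = 21, or 7 + 20 + 1 + 3 = 31. With a composite biomarker each total falls by 2, to 19 or 29. The subset with more than 7 dosing days is left out because it is not defined at baseline; including it gives 22 or 32.

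**5. Events available.** SAP 4.10.1.1.3 reports that under 2% of subjects had been hospitalized. On the planned 668 that is fewer than 0.02 × 668 = 13.4, so at most 13 events, before splitting by subset and then by age and the 2 × 3 × 3 = 18 randomization strata. That figure is for hospitalization, not the full composite.

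**6. Chance of at least one subset p < 0.025 with no drug effect.** The SAP states no alpha for these tests, so 0.025 is taken from the primary test. Expected false positives are 21 × 0.025 = 0.53 to 31 × 0.025 = 0.78. If the tests were independent, the chance of at least one would be 1 − 0.975²¹ = 41% to 1 − 0.975³¹ = 54%. The subsets overlap heavily, so this is only an upper reference. Simulated null trials of 668 subjects, with assumed prevalences, give:

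| Method | 1.5% events | 2% events | 3% events | 6% events |
|---|---|---|---|---|
| Stratified CMH, 32 subsets | 13% | 17% | 22% | 25% |
| Stratified CMH, 22 subsets | 9% | 13% | – | – |
| Unstratified score test, 31 subsets | – | 17% | 20% | 26% |
| Unstratified score test, risk unrelated to subset | 8–14% (1.5–2%) | same cell | 13–16% | 20–23% |
| Exact one-sided test | 1.5–4% (1.5–2%) | same cell | – | – |

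Assumptions: age 50 or over in about 27% in the 31-subset run, hypertension 12–40%, diabetes 6–20%, smoking 30%, raised biomarkers 25–40%. The CMH rows used similar values, with age coded at a 50-year cut-off. The 22- and 32-subset rows include the dosing-days subset; dropping it does not change the picture.

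Relative to 2.5%: 8/2.5 ≈ 3-fold to 17/2.5 ≈ 7-fold at up to 2% events, and 25/2.5 = 10-fold at 6%. At 1.5–2% events, about 7–14% of null trials show a significant subset while the primary test is not significant.

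**The case against.** The strongest reply is that the exploratory clause in 4.10.1.3 covers all subgroup analyses, so if these are subgroup analyses they are already exploratory. SAP 4.10.3 nowhere calls them confirmatory, allots them no alpha and rests no claim on them. That stands. A reader might infer that the plan promotes these subsets to confirmatory status, or that the type I error of the primary test is damaged. The documents support neither. What remains is a direct conflict over whether p-values are computed within these groups, and a label that does not fit.

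A second reply is that 4.10.1.3 concerns the primary variable while 4.10.3 concerns a secondary one. This fails, because the secondary variable is the complement of the primary.

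Third, a false-positive subset is not likely in the ordinary sense. That also stands. The simulated figures are well below one half, and the 41–54% range needs an independence that these subsets do not have. At the event frequency the SAP reports, the lower columns of the table are the relevant ones.

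Fourth, the age-plus-timing subset adds little, since inclusion criteria 5 and 6 already impose those windows. It largely repeats the test in patients aged 50 or over. This is true, and is one reason why the tests overlap so much.

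Finally, the SAP revision history dates these subsets to March 2022, and a reader might infer that they were chosen from results by arm. The documents report only an overall hospitalization frequency and do not support that inference.

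**Conclusion.** Wrong as written: SAP 4.10.1.3 and 4.10.3 contradict each other on formal testing within subgroups. This rests on the text alone and on no simulation.

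The conflict affects 21 baseline-defined subset tests if each age-condition pair has one reading, and 31 if both are run (two fewer with a composite biomarker). Applying *and/or* to all ten pairs extrapolates from the SAP's two obesity examples. The added false-positive risk is about three to seven times the nominal 2.5% at event frequencies up to 2%, and about ten times at 6%. It depends on the assumed prevalences, overlap and test, and with an exact test it could be close to nominal. The conclusion on the primary endpoint is unaffected. What changes is which tests are run and what may be said about a subset.

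**What to change.** - Move the baseline-defined subsets of SAP 4.10.3 under 4.10.1.3 and call them exploratory subgroup analyses.
- State for each age-condition pair whether it is *and* or *or*, and whether the three biomarkers are separate subsets or one composite.
- In the forest plots already planned, show event counts, estimates and confidence intervals by arm, without within-subset p-values. One treatment-by-factor interaction test per factor is optional.
- Add a sentence that no efficacy claim rests on a subset.
- Keep the per-protocol, complete-case and missing-data analyses of SAP 4.10.2 as sensitivity analyses. Protocol 10.5.1.3 itself names the first two as such, so the term should not be confined to the full mITT set.
- Treat the subset with more than 7 dosing days separately, as a supplementary analysis, and note that it conditions on a post-randomisation variable. Under Protocol 6.3.1, dosing may end because of drug-related events and is discretionary after hospitalization, so the two arms may be selected differently.

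The cost is SAP wording and fewer p-values in outputs already planned. No new data, subjects or analyses are needed.

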## Annotation:

1. Inclusion/Exclusion review: every subject needs to meet all inclusion and exclusion criteria. The eligibility checklist needs to be signed by the investigator or sub-investigator.
2. Demographics: includes age, gender, race, and ethnicity.
3. Pre-existing conditions and medical history: obtained from interview or available information and including timing of exposure and onset of symptoms suggestive of SARS-CoV-2 infection.
4. NIAID ordinal scale to be completed daily through Day 28 or 14 days after last dose. This information can be collected from questionnaire; reported events; or directly from the patient.
5. Prior treatments within last 30 days.
6. Physical exam (PE): Full physical exam should be done at screening visit. For the subsequent visits, symptom directed PE can be done per investigator's discretion. If the result is clinically significant, the PE result should be recorded in eCRF.
7. Vital sign: documentation of hospital-based exam is acceptable. Vital signs include body temperature, pulse rate, systolic and diastolic blood pressure, respiratory rate. For screening visit, SpO2, and supplemental oxygen flow rate, FiO2 if known and method of delivery if applicable, also need to be recorded. Record blood pressure and SpO2 while subject is at rest.
8. Nasopharyngeal (NP) swabs: Only NP swab sample is acceptable. The method of taking samples should be consistent for each subject during the whole period of this study. This does not need to be the same before screening visit, when the subject is first time confirmed SARS-CoV-2 positive at local laboratory and/or Point of Care testing. Sample for first positive test must be collected within 3 days prior to start of dosing. Local laboratory and/or Point of Care testing are acceptable.
9. Randomization: randomization should be via the Interactive Voice/Web (IxRS) Response System. Randomization should be done after confirmation the subject meets all inclusion/exclusion criteria. Drugs and Diary Dispense should occur after randomization. It is allowed for the subject to take the drug on the

same day of the screening visit after confirmation of eligibility and randomization (the screening visit is counted as D1 too). The Subject Diary should start to be completed.

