## 2 RATIONALE

### 2.1 Study Rationale and Purpose

The glycoprotein spikes on the surface of SARS-CoV-2 utilize membrane ACE2 receptors and TMPRSS2, to enter the host cells (6). Thus, targeting the expression or activity of ACE2 or TMPRSS2 plays a critical role in reducing the pathogenicity of coronavirus infection, GT0918 can down-regulate the ACE2 and TMPRSS2 expression in prostate, lung cancer cell lines and lung epithelial cell lines. Furthermore, the clinical study of GT0918 in Brazil for COVID-19 (NCT04446429) showed a clinically meaningful SARS-CoV-2 viral load reduction and clearance, decreased the hospitalization rate significantly in the GT0918 group compared to the placebo group. Therefore, GT0918 may be an efficient option to improve clinical outcome and reduce the rate of hospitalization in COVID-19 infected patients. Since SARS-CoV-2 replication is greatest just before or soon after symptom onset, GT0918 is likely to be most effective when used early. Therefore, in this study, GT0918 will be administered to evaluate the efficacy and safety in COVID-19 infected outpatients with mild or moderate symptoms.

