#### 4.1.1 Screening and Randomization

After signing the study ICF, the screening assessments will be done within 1 day prior to randomization for selected assessments (See SoA) for the list of assessments to be performed).

The investigator will review symptoms, risk factors and other inclusion and exclusion criteria to confirm subject's eligibility.

Subjects will be randomized into 1 of 2 arms with 1:1 ratio, each will receive an interventional treatment/placebo.

Randomization will be stratified by the following factors:

- Sex: Male or Female
- Race and ethnicity (non-Hispanic White or others /Hispanic or Latino /non-Hispanic Black)
- Number of risk factors 0, 1-2,  $\geq 3$  (based on CDC defined conditions <https://www.cdc.gov/coronavirus/2019-ncov/need-extra-precautions/people-with-medical-conditions.html>). Adults with the following conditions are at increased risk of severe illness from the virus that causes COVID-19:
  - Age  $\geq 65$  years
  - Cancer
  - Chronic kidney disease
  - Chronic lung diseases, including COPD (chronic obstructive pulmonary disease) asthma (moderate to severe), interstitial lung disease, cystic fibrosis, and pulmonary hypertension
  - Dementia or other neurological conditions
  - Down Syndrome
  - Heart conditions, such as heart failure, coronary artery disease, or cardiomyopathies or hypertension
  - Immunocompromised state (weakened immune system) from solid organ transplant
  - Liver disease
  - Overweight and Obesity (body mass index [BMI]  $\geq 25$  kg/m^2)
  - Sickle cell disease or thalassemia
  - Smoking, current or former
  - Diabetes Type 1 or type 2)
  - HIV infection
  - Solid organ or blood stem cell transplant
  - Stroke or cerebrovascular disease, which affects blood flow to the brain

- Substance use disorders
- Others per most updated list from CDC website as above

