### 5.2 Inclusion Criteria

Subjects are eligible to be included in the study only if all the following criteria apply:

1. The subject or legally authorized representative give signed informed consent which includes compliance with the requirements and restrictions listed in the ICF and in this protocol.
2. Understand and agree to comply with planned study procedures.
3. Male and non-pregnant female subjects with age  $\geq 18$  years of age at the time of randomization.
4. Are currently not hospitalized.
5. Have one or more COVID-19-related symptoms within 5 days of symptoms onset ((FDA COVID-19-Related symptom guidance, See Appendix 2, available at: <https://www.fda.gov/media/142143/download>)
6. Must have first positive SARS-CoV-2 viral infection determination (has laboratory-confirmed SARS-CoV-2 infection as determined by PCR, or other commercial or public health assay in any specimen)  $\leq 3$  days prior to start of the first dose.
7. Women of child-bearing potential, defined as all women physiologically capable of becoming pregnant, unless they are using highly effective contraception, as shown below, throughout the study and for 3 months after stopping GT0918 treatment. Highly effective contraception methods include:
  - Total Abstinence (when this is in line with the preferred and usual lifestyle of the patient. Periodic abstinence (e.g. calendar, ovulation, symptothermal, post-ovulation methods) and withdrawal are not acceptable methods of contraception, or
  - Use of one of the following combinations (a+b or a+c or b+c):
    - a: Use of oral, injected or implanted hormonal methods of contraception or other forms of hormonal contraception that have comparable efficacy (failure rate  $< 1\%$ ), for example hormone vaginal ring or transdermal hormone contraception.
    - b: Placement of an intrauterine device (IUD) or intrauterine system (IUS);
    - c: Barrier methods of contraception: Condom or Occlusive cap (diaphragm or cervical/vault caps) with spermicidal foam/gel/film/cream/vaginal suppository;

- Female sterilization (have had prior surgical bilateral oophorectomy with or without hysterectomy) or tubal ligation at least six weeks before taking study treatment. In case of oophorectomy alone, only when the reproductive status of the woman has been confirmed by follow-up hormone level assessment;

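### The primary-endpoint timing subgroups are cut at the eligibility limits, so they give almost no early-versus-later contrast; the SAP's own 3-day onset split is not applied to the composite

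*SAP*

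**What the plan says.** SAP 4.10.1.3 lists subgroups in which the primary endpoint may be summarized and shown in a forest plot. Two concern timing:

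- "Days from symptom onset to study randomization", in levels of up to 5 days and more than 5 days;
- "Days from the Positive SARS-CoV-2 Prior to First Dosing", in levels of up to 3 days and more than 3 days.

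Protocol 5.2 sets the entry conditions. Criterion 5 reads "Have one or more COVID-19-related symptoms within 5 days of symptoms onset". Criterion 6 requires the first positive determination no more than 3 days before the first dose, and note 8 to the Schedule of Activities repeats this: "Sample for first positive test must be collected within 3 days prior to start of dosing".

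SAP 4.10.3 divides the same onset-to-randomization interval at 3 days for Cox models of time to sustained viral reduction and time to hospitalization. Viral clearance, symptom resolution and symptom improvement take over those models. SAP 4.11.3 stratifies time to adverse events of special interest by the same 3-day category.

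SAP 4.10.3 also tests hospitalization percentage in subjects aged 50 or over with onset within 5 days and "days from the positive SARS-CoV-2 Prior to first dosing" within 3 days. Age 50 or over alone is already a listed subset.

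**The concern.** A subgroup analysis informs only if both levels hold a useful number of subjects. When the cut equals the entry limit, one level is close to the whole trial and the other holds mostly subjects who should not have been enrolled. The forest plot then shows a row that repeats the overall estimate beside a row with almost no data.

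Timing is not incidental here. Protocol 2.1 says "GT0918 is likely to be most effective when used early", and Protocol 10.5.1.4 puts time from symptom onset first in its subgroup list without fixing a cut. The SAP could therefore have chosen an informative cut without departing from the protocol. At stake is the only planned look at whether the effect on the composite primary endpoint varies with time since onset or since the positive test. A smaller matter is that the age-and-timing subset of 4.10.3 may appear as a separate finding when it nearly duplicates another.

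**Working it through.** **Plan's own figure.** SAP 4.12 gives 668 subjects for about 90% power, 97% versus 91%, one-sided 0.025, with one interim at half the information. For a fixed design with pooled variance under the null:

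n per arm = [z(0.975)·√(2·0.94·0.06) + z(0.90)·√(0.97·0.03 + 0.91·0.09)]² / 0.06² = [1.960·0.3359 + 1.282·0.3332]² / 0.0036 ≈ 328, or 656 in total.

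With 334 per arm the fixed-design power is 0.906. With O'Brien-Fleming-type spending (0.0015 at the interim, 0.0245 at the end) it is 0.903 to 0.908. The figure of 668 reproduces. The point below does not depend on it except as a denominator.

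**Cuts against entry limits.**

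| Factor | Subgroup cut (SAP 4.10.1.3) | Entry limit (Protocol 5.2) | Reference date |
|---|---|---|---|
| Symptom onset | 5 days | 5 days | Subgroup: randomization. Criterion: not stated |
| Positive test | 3 days | 3 days | First dose in both |

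For the positive test the reference date is the same, so a subject above 3 days does not meet criterion 6 as now written. For onset there is some slack. Protocol 4.1.1 says "the screening assessments will be done within 1 day prior to randomization", so a subject at 5 days at screening could be at 6 days at randomization without breaching criterion 5 read at screening.

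**Who can be in the upper levels.** The mITT set (SAP 4.5) keeps every randomized and dosed subject, and Protocol 7.1.3.1 lets an inadvertently enrolled subject continue with sponsor approval. The upper levels can therefore hold some subjects.

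**Size.** The documents give no distribution of either interval, so the shares below are assumptions. The planned average failure rate is (3% + 9%)/2 = 6%. SAP 4.10.1.1.3 reports under 2% hospitalization observed. That is one component only, and 2% is used here as a low illustrative rate.

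| Split | Assumed share | Subjects | Events at 6% | Events at 2% |
|---|---|---|---|---|
| Present cuts, upper level | 0 to 5% of 668 | 0 to 33 (0 to 17 per arm) | 0 to 2.0 | 0 to 0.7 |
| Onset at 3 days, each level | 30 to 70% of 668 | 200 to 468 | 12 to 28 | 4 to 9 |

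Examples: 0.05·668 = 33.4 and 33.4·0.06 = 2.0; 0.30·668 = 200.4 and 200.4·0.06 = 12.0. Under the first assumption the lower level of each present cut holds 95 to 100% of subjects.

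**Overlap of the age subset.** If at most 5% of subjects aged 50 or over exceed each limit, at least 100 − 5 − 5 = 90% of them meet both timing conditions. The restricted subset is then at least nine tenths of the subset already listed, and both receive the same one-sided CMH test.

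**The case against.** The strongest reply has four parts.

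- **The SAP does examine early treatment.** The 3-day onset split is planned for time to hospitalization (all-cause and COVID-19-related) and for viral and symptom time-to-event endpoints, and hospitalization is a component of the primary endpoint. This stands. A reader might infer that early-treatment benefit cannot be examined at all; the documents do not support that. The gap is the composite primary endpoint, plus days from positive test, which has no split inside the eligible range for any endpoint.
- **The upper levels are not shown to be empty.** This also stands. A reader might infer that one level must be empty or hold only protocol deviators. Dosed ineligible subjects remain in the mITT, criterion 5 names no reference date, and screening may precede randomization by a day.
- **The cuts may be meant to compare subjects inside and outside the intended window.** That is a legitimate use, and the age subset could be read the same way. The SAP does not say so, and it presents both splits as ordinary subgroups.
- **The gain is small.** Subgroups are optional, exploratory and unpowered, with no formal test within subgroup. Protocol 2.1 uses the early-treatment argument to justify the population enrolled, and it promises no comparison within the 5-day window. With 4 to 9 events per level at a 2% rate, a better cut would describe but not test a timing effect. This limits the severity; it does not make the present cuts informative.

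**Conclusion.** The point holds at low severity. That both primary-endpoint timing cuts coincide with the entry limits is certain from the text. That the upper levels are sparse is likely but not shown: it rests on few subjects having been randomized outside the window, and the documents give no count. Under an assumed 0 to 5% the upper level has at most about 33 subjects and 2 events, and the lower level is practically the whole mITT set. The SAP is also inconsistent, since it divides the same onset interval at 3 days for other endpoints and gives no reason for using 5 days here. The near-duplication of the age-50 subset rests on the same assumption. Neither the primary test nor its alpha is affected.

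**What to change.** - In SAP 4.10.1.3, use up to 3 versus more than 3 days from onset to randomization for the primary-endpoint forest plot, as in the SAP's own Cox models.
- For days from positive test to first dose, pre-specify a cut inside the 0 to 3 day range before unblinding. The documents point to no particular value; the pooled, blinded distribution of days could guide the choice.
- If the 5-day and 3-day splits are kept, label them as an eligibility-window check and show the number of subjects in each level.
- In SAP 4.10.3, either drop the timing conditions from the subset aged 50 or over, or report it as an eligibility-restricted check on the listed age subset.

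The cost is SAP wording with a short documented reason, because version 2.0 was already final on 14 March 2022. Protocol 7.1.1.3 already collects days from symptom onset and the date of the positive test, and Protocol 10.5.1.4 fixes no onset cut, so neither new data nor a change to the protocol's subgroup list is needed for the onset split. Any re-cut made after unblinding should be labelled post hoc.
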